- A1C = glycated hemoglobin; ECG = electrocardiogram; eGFR = estimated glomerular filtration rate; FSH = follicle-stimulating hormone; hs-CRP = high sensitivity C-reactive protein; hs-IL-6 = high sensitivity interleukin 6; Lp(a) = Lipoprotein(a); OxPL/ApoB = oxidized phospholipids on apolipoprotein B 100; PK = pharmacokinetics; PROMIS = Patient-Reported Outcomes Measurement Information System; **W = week**
- ^a Clinical outcome assessments should always be performed first at study visits, with study treatment administration performed last, except for days when post-dose PK samples are collected (day 1, week 12, week 24, and week 36).
- ^b Safety Follow-up calls are scheduled at 1 day after weeks 12, 24, and 36 visits.
- ^c **Survival status checks should be performed for any subject who withdraws consent, or subjects considered lost to follow-up, or subjects unwilling to continue schedule of assessments, to the extent permitted by local law. Refer to Section 8.2.3.2 for additional details.**
- ^d **After end of study, if the investigator becomes aware of serious adverse events suspected to be related to investigational product, then these serious adverse events will be reported to Amgen. Please refer to Section 8.2.4.1.3 for additional details.**
- ^e Additional on-treatment pregnancy testing may be performed at the investigator's discretion if there is suspicion that a female subject is pregnant or per local laws and regulations. Urine pregnancy test can be completed by study staff or local laboratory.
- ^f Blinded laboratory results: Lp(a), lipid panel, hs-CRP, hs-IL-6, ApoA1, and ApoB laboratory result will be provided to sites at Screening and Day 1, but will be blinded after Day 1.
- ^g Biomarker development samples will be obtained from the biomarker discovery blood draw, for subjects who consent.
- ^h Optional pharmacogenomic sample will be derived from the biomarker plasma draw.
- ⁱ Additional PK samples will be collected in a subset of subjects (N = approximately 75) who consent to the optional PK sub-study. Refer to Table 1-2 below for additional time points required for these subjects.
- ^j Collected at the end of study visit if this visit occurs prior to week 48.
- ^k **After week 48 there will be an extended safety follow-up without further dosing with investigational product for a minimum of 24 weeks.**
- ^l **Per Protocol Amendment 2, some subjects will have an End of Study visit after week 72.**

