5.3 Other Study Related Definitions

Analytical Study Week Assignments

Analytical windows will be used to assign parameter measurements to study weeks. The algorithm is provided in [Appendix A](#).

Actual Treatment Group

A subject's actual treatment group is the randomized treatment group, unless the subject receives treatment throughout the study that is different than the randomized treatment group assignment, in which case the actual treatment group is the treatment received.

Investigational Product (IP)

Olpasiran SC 10 mg Q12W, 75 mg Q12W, 225 mg Q12W, 225 mg Q24W and placebo SC Q12W.

Study Exposure Period in Months

For each randomized subject, Study Exposure Period = (EOS date – Randomization Date + 1) / 365.25 * 12

IP Exposure Period in Months

IP Exposure Period = [min (Last IP Dose Date + 84 days, EOS Date) – First IP Dose Date + 1] / 365.25 * 12

Treatment Emergent Adverse Event in Treatment Period

Events categorized as Adverse Events (AEs) starting on or after first dose of investigational product as determined by “Did event start before first dose of investigational product” equal to No or missing on the Events eCRF and up to the End of Treatment Period date, or EOS date for subjects who early discontinue the study during the treatment period.

Treatment Emergent Adverse Event in Extended Safety Follow-up Period

Events categorized as Adverse Events (AEs) starting on or after first dose of investigational product (as determined by “Did event start before first dose of

investigational product” equal to No or missing on the Events eCRF) and on or after the Extended Safety Follow-up Period Start Date, and up to the EOS date.

Reflexive Approach for LDL-C and VLDL-C

Reflexive approach for LDL-C and VLDL-C is only applicable for the central lab data. For all analyses related to LDL-C and VLDL-C, unless specified otherwise, the following reflexive approach will be used.

When calculated LDL-C is less than 40 mg/dL or triglycerides are > 400 mg/dL, the ultracentrifugation (UC) LDL-C value from the same blood sample will be used instead of calculated LDL-C and the UC VLDL-C value from the same blood sample will be used instead of calculated VLDL-C, if available.

6. Analysis Sets

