7.1 Interim Analysis and Early Stopping Guidelines

An administrative interim analysis will be performed when approximately 240 subjects have had the opportunity to complete week 24 assessments or have early terminated. At that point, approximately 120 subjects may have had the opportunity to complete week 36 assessments or have early terminated. The study continues per protocol as planned regardless of the data from the administrative interim results.

Interim analysis results will be reviewed by an Interim Analysis Review Steering Committee (IARSC) which consists of internal experts, who are or will thereafter be independent of the study team. Further detail regarding the interim analysis process in protecting trial integrity is provided in the IARSC Charter.

In addition to routine pharmacovigilance monitoring by Amgen, a Data Review Team (DRT) has been established to review the accumulating data from this study to ensure there is no avoidable increased risk for harm to subjects. The DRT is internal to Amgen but external to olpasiran teams. In order to maintain the trial integrity, the unblinded data reviewed by the DRT will be restricted and not accessible by the olpasiran team. Further detail regarding the DRT is provided in the DRT Charter.

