9.1 General Considerations

Unless specified otherwise, efficacy analyses will be performed on the FAS by randomized treatment group, and safety analyses will be performed on the FAS by actual treatment group.

For the Primary Analysis (as described in Section 7.2), all data up to the primary analysis data cut-off date will be included. Based on the snapshot for the primary analysis, efficacy and safety analyses will be performed. Testing will be performed for endpoints defined up to week 36. Descriptive summary will be provided for all available visits by period (ie. Treatment period and extended safety follow-up period).

For the End of Treatment Period Analysis (as described in Section 7.3), all data up to the end of treatment period analysis cut-off date will be included. Testing will be performed for endpoints defined up to week 48. Descriptive summary will be provided for all available visits by period (ie. Treatment period and extended safety follow-up period).

For the Final analysis (as described in Section 7.4), all efficacy and safety analyses during the extended follow-up period will be performed based on the snapshot for the final analysis.

Subject disposition, demographics, baseline characteristics, and exposure to IP will be summarized.

All categorical variables will be summarized using the number and percent of subjects and all continuous variables will be summarized using mean, standard error or standard deviation, median, minimum, maximum, and number of subjects with observations.

Multiplicity Adjustment Method:

The Hochberg procedure will be used to control the type I error for multiple comparisons between active and placebo groups in the primary endpoint. The primary endpoint includes percent change in Lp(a) from baseline at week 36 for olpasiran SC Q12W groups and placebo. Percent change in Lp(a) from baseline for Q24W group is defined as exploratory endpoint.

A summary of the analyses for each planned analysis can be found in Table 2.

Table 2. Summary of Analyses

Analyses	Primary Analysis (all data up to primary analysis data cut-off date)	End of Treatment Period Analysis (all data up to End of Treatment Period Analysis data cut-off date)	Final Analysis (all data based on final snapshot)

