Efficacy	
 • Repeated measures model for primary endpoint, secondary endpoints defined at week 36, and exploratory endpoints of percent change from baseline in Lp(a), LDL-C and ApoB up to week 36. • Multiplicity adjustment for primary endpoint, as described above in Multiplicity Adjustment Method • Sensitivity analysis for primary endpoint using non-parametric (Quade test) approach based on CAS • Cochran-Mantel Haenszel (CMH) test adjusted by the stratification factors will be used for exploratory endpoints of Lp(a) achievements 	
 • Repeated measures model for primary endpoint, secondary endpoints defined at week 36 and week 48 and exploratory endpoints of percent change from baseline in Lp(a), LDL-C and ApoB up to week 48. Testing is performed up to week 48. • Multiplicity adjustment for primary endpoint, as described above in Multiplicity Adjustment Method • Sensitivity analysis for primary endpoint using non-parametric (Quade test) approach based on CAS • Cochran-Mantel Haenszel (CMH) test adjusted by the stratification factors will 	
 • Descriptive summary for efficacy endpoints in the extended follow-up period

	
(including achievement of Lp(a) < 125nmol/L) up to week 36
 
 • Descriptive summary for all efficacy endpoints by period (ie. Treatment period and extended safety follow-up period) 	
be used for exploratory endpoints of Lp(a) achievements (including achievement of Lp(a) < 125nmol/L) up to week 48
 
 • Descriptive summary for all efficacy endpoints by period (ie. Treatment period and extended safety follow-up period) 	
Safety	
 • Summary by actual treatment group by period (ie. Treatment period and extended safety follow-up period) 	
 • Summary by actual treatment group by period (ie. Treatment period and extended safety follow-up period) 	
 • Summary by actual treatment group in the extended follow-up period

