Appendix A. Analytical Study Week Assignments

Selected endpoints will be summarized by scheduled study visits in descriptive analyses. Since the actual visits may not exactly coincide with their scheduled visit day, the actual visit day is mapped to the study visit generally by non-overlapping consecutive intervals covering the entire time continuum. The mapping intervals for all distinct schedules are summarized in the following table.

Handling multiple records assigned to an analytical study week:

If there is more than one record in a study week interval, the analytical record for that specific study week will be defined as the record closest to the scheduled visit day of that specific study week ($7 \times \text{study week} + 1$). If two records are equidistant from the scheduled day, then the earlier record will be chosen. If there are multiple records on the same day, the last record will be used.

Analytical Study Week	Scheduled Visit Day	Physical, Neurological, and Muscular Examination, Vital Signs, Urine Pregnancy Test, Anti-Olpasiran-Antibody, PROMIS General Health	Physical measurement (weight only)	Fasting Lipids and Lp(a)	Glucose, ApoA1, ApoB, VLDL-C, Coagulation, Hematology, Hemoglobin A1C, Chemistry including hs-CRP, eGFR, Urinalysis
Day 2	2			(1, 15]	
Week 4	29			(15, 42]	(1, 56]
Week 8	57			(42, 70]	
Week 12	85	(1, 126]		(70, 98]	(56, 126]
Week 16	113			(98, 126]	
Week 20	141			(126, 154]	
Week 24	169	(126, 210]		(154, 182]	(126, 210]
Week 28	197			(182, 210]	
Week 32	225			(210, 238]	
Week 36	253	(210, 294]		(238, 266]	(210, 294]
Week 40	281			(266, 294]	
Week 44	309			(294, 322]	
Week 48	337	(294, 420]	(1, 420]	(322, 378]	(294, 420]
Week 60	421			(378, 462]	
Week 72	505	(420, 546]	(420, 546]	(462, 546]	(420, 546]
Week 84	589			(546, 630]	
Q12W ^a	n*7+1			((n-6)*7, (n+6)*7]	
> Week 72	Scheduled visit day	> 546	> 546	.. ^b	> 546

^a For Q12W scheduled visit, week n can have possible values of 96+12*m, where m=0, 1, 2, 3, ... until the subject **has completed study** or subject has discontinued from the study.

^b For Lipids and Lp(a), all visits occurred after week 84 will be mapped to Q12W window.

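### Events in the extended follow-up are planned only as crude percentages although follow-up length varies and an objective asks for event rates, and the treatment-period end date has no rule for a subject who misses week 48 but stays on study

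*SAP*

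**What the plan says.** **Length of follow-up.** Table 1-1 of the protocol places the end-of-study visit at week 72. Its footnotes make this a minimum: "After week 48 there will be an extended safety follow-up without further dosing with investigational product for a minimum of 24 weeks", and "Per Protocol Amendment 2, some subjects will have an End of Study visit after week 72". SAP Appendix A has lipid and Lp(a) windows for week 84 and later ("For Q12W scheduled visit, week n can have possible values of 96+12*m"), and an open-ended row after day 546 for the other parameters.

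**Event summaries.** SAP 5.3 takes follow-up TEAEs that start "on or after the Extended Safety Follow-up Period Start Date, and up to the EOS date". SAP 9.6.1 reports adverse events, and SAP 9.5.3 reports positively adjudicated events, as subject incidence. Table 2 in SAP 9.1 asks at the primary and end-of-treatment analyses for "Descriptive summary for all efficacy endpoints by period (ie. Treatment period and extended safety follow-up period" and, for safety, "Summary by actual treatment group by period (ie. Treatment period and extended safety follow-up period". By default, "safety analyses will be performed on the FAS by actual treatment group". SAP 2.1 lists the estimation of cardiovascular event rates, including programme-wide aggregation, as an exploratory objective. SAP 5.3 defines a Study Exposure Period over the whole study, but no event analysis uses it.

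**Period boundary.** SAP 5.1 words two cases for the End of Treatment Period Date: the latest week-48 assessment date if there is one, and the EOS date for a subject who left before week 48. It then condenses both into the minimum of the two dates. Follow-up starts the next day.

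**The concern.** A percentage of subjects with an event depends on how long they were watched. Where length differs between subjects, or between one data snapshot and the next, the percentage moves even if the underlying rate does not. It therefore does not answer an objective worded in terms of rates, and percentages over different durations cannot sensibly be pooled across a programme.

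The boundary rule decides which table an event enters. A subject with no week-48 assessment who remains on study fits neither worded case. The case is foreseeable: Protocol 8.1.2 asks subjects who stop study treatment to continue visits, and SAP 8.3.1 anticipates missed visits.

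**Working it through.** **1. Durations.** Protocol 4.4.2 gives about 76 weeks per subject: 4 + 48 + 24 = 76. This reproduces, and it uses the minimum follow-up. With the Appendix A formula, day = 7 × week + 1:

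- week 48 = day 337
- week 72 = day 505, so 505 − 337 = 168 days (24 weeks) of follow-up
- week 84 = day 589, so 589 − 337 = 252 days (36 weeks)
- week 96 = day 673, so 673 − 337 = 336 days (48 weeks)

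**2. One rate, several percentages.** The documents give no event rate. Assume a constant hazard and a 24-week risk p of 5% or 10%. Then λ = −ln(1 − p)/24 per week, the risk over w weeks is 1 − exp(−λw), and the rate per 100 subject-years is λ/7 × 365.25 × 100.

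| Assumed 24-week risk | 36 weeks | 48 weeks | Rate per 100 subject-years |
|---|---|---|---|
| 5% | 7.4% | 9.8% | 11.2 |
| 10% | 14.6% | 19.0% | 22.9 |

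Expected time at risk to first event or week w is (1 − exp(−λw))/λ. Expected first events divided by this time give λ for every w, so the person-time rate stays put while the percentage nearly doubles.

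**3. Primary snapshot.** SAP 7.1 expects the interim when about 240 subjects have reached week 24, at which point "approximately 120 subjects may have had the opportunity to complete week 36 assessments or have early terminated". That implies about 240 − 120 = 120 randomised in 12 weeks, or 10 per week. Assume that pace throughout.

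- The snapshot comes when the last subject reaches week 36. Subjects randomised in the final 12 weeks have not reached week 48: 120/290 = 41% have no follow-up time. A pace of 60 to 180 per 12 weeks (assumption) gives 60/290 = 21% to 180/290 = 62%.
- Randomisation takes 290/10 = 29 weeks, so the first subject is at week 36 + 29 = 65 and has 65 − 48 = 17 weeks of follow-up. No one has 24.
- With λ = 0.00439 per week (the 10% case) and entrants' follow-up spread evenly over 0 to 17 weeks, the mean risk is 1 − (1 − exp(−17λ))/(17λ) = 3.6%. Over the whole FAS it is 3.6% × 170/290 = 2.1%.

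So a rate that shows as 10% over 24 weeks would show as 3.6% of entrants, or 2.1% of the FAS, at this snapshot.

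**4. Boundary date.** Take a subject with no week-48 assessment and EOS at week 72.

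- If the missing date is ignored, the minimum is day 505. The treatment period gains 168 days (168/337 = 50%), and follow-up starts the day after the subject has left.
- If a missing date makes the result missing, the subject has no boundary.
- At the primary snapshot, an ongoing subject between weeks 36 and 48 has neither date. At the end-of-treatment snapshot, the same holds for an ongoing subject who missed week 48.
- Ongoing subjects already in follow-up have no EOS date to close the TEAE window.

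**The case against.** These are descriptive safety and exploratory outputs in arms of about 58, with no test attached, and subject incidence is the usual format. The listed endpoint is simply adjudicated events, and programme-level aggregation lies outside this SAP. Week 72 is the scheduled end, and the documents do not say how many subjects go past it. The FAS is a default, and nothing states that subjects who never entered follow-up stay in the follow-up denominator. SAP 9.1 limits each analysis to its data cut-off, which closes open windows in practice. The treatment period already includes off-drug time for subjects who stop dosing and keep attending.

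Most of this limits the size of the point, and all of it argues for a low severity. It does not supply a rate for an objective that asks for one, name the follow-up denominator, or bring the cut-off into the definitions in SAP 5.1 and 5.3.

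A reader might infer a stronger problem: that follow-up length differs by arm and biases the comparison with placebo. The Amendment 3 rationale says follow-up had been linked to Lp(a) recovery, which could differ by arm. That requirement was removed, and the current text gives no lengths by arm, so arm-related imbalance is possible but not shown. A reader might also infer that the wide Appendix A windows push the boundary well past day 337. The closest-record rule there makes that remote; only the ambiguity between nominal visit and window remains.

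**Conclusion.** The point stands as minor.

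- **Event summaries.** The planned percentages do not estimate the rates named in the objective, and they change with follow-up length and snapshot. The sizes shown rest on an assumed constant hazard and assumed event risks. The share without follow-up at the primary snapshot (about 41%, range 21% to 62%) rests on an assumed recruitment pace. The end-of-treatment analysis waits until all subjects have had the opportunity to complete week 48, so that share does not carry over to it.
- **Boundary date.** The rule has a gap. Each affected subject ending at week 72 would have 168 days placed in the wrong period. The number affected is not given and is likely to be small at the final analysis.

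The documents do not support a claim of between-arm bias, and the efficacy tests at weeks 36 and 48 are untouched.

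**What to change.** **SAP 9.5.3 and 9.6.1**
- Keep the incidence columns and the split by period, but use subjects who entered follow-up as the denominator for that period.
- Add first-event rates per 100 subject-years for adjudicated events in each period and for follow-up TEAEs. Person-time runs from the start of the period to the earliest of first event, end of period, EOS or data cut-off.
- Summarise the number entering and the follow-up time by arm.

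**SAP 5.1 and 5.3**
- State that the week-48 assessments are those of the nominal visit (or of the Appendix A window, if that is intended).
- When none exists, set the End of Treatment Period Date to min(EOS date, data cut-off date, study day 337). Day 337 is the scheduled week-48 day, and it equals the week-36 day plus the 84 days used in the IP Exposure Period: 253 + 84 = 337.
- Close the follow-up TEAE window at min(EOS date, data cut-off date).

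**Cost.** SAP wording, a few table columns and a short derivation; no new data. The rates are easiest to interpret if the hazard is roughly constant, and day 337 may fall slightly before a late visit would have.

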6.1 Full Analysis Set

Full analysis set (FAS) includes all randomized subjects who received at least one dose of investigational product.

FAS will be used to perform the efficacy analysis based on randomized treatment group, and the safety analysis based on actual treatment group (defined in section 5.3).

6.2 Completer Analysis Set

The completer analysis set (CAS) includes subjects in the FAS who adhered to the scheduled IP regimen, and have observed value for the primary endpoint. The completer analysis set will be used in sensitivity analysis of the primary endpoint.

7. Planned Analyses

7.1 Interim Analysis and Early Stopping Guidelines

An administrative interim analysis will be performed when approximately 240 subjects have had the opportunity to complete week 24 assessments or have early terminated. At that point, approximately 120 subjects may have had the opportunity to complete week 36 assessments or have early terminated. The study continues per protocol as planned regardless of the data from the administrative interim results.

Interim analysis results will be reviewed by an Interim Analysis Review Steering Committee (IARSC) which consists of internal experts, who are or will thereafter be independent of the study team. Further detail regarding the interim analysis process in protecting trial integrity is provided in the IARSC Charter.

In addition to routine pharmacovigilance monitoring by Amgen, a Data Review Team (DRT) has been established to review the accumulating data from this study to ensure there is no avoidable increased risk for harm to subjects. The DRT is internal to Amgen but external to olpasiran teams. In order to maintain the trial integrity, the unblinded data reviewed by the DRT will be restricted and not accessible by the olpasiran team. Further detail regarding the DRT is provided in the DRT Charter.

7.2 Primary Analysis

Primary analysis will be performed when all randomized subjects have had the opportunity to complete the week 36 assessments or have early terminated. At that time, the database related to the primary analyses will be cleaned, processed and a snapshot will be taken.

Only an unblinded team will be unblinded at the primary analysis. Individuals who will remain involved in the conduct of the study will remain blinded.

7.3 End of Treatment Period Analysis

The end of treatment period analysis will be performed when all randomized subjects have had the opportunity to complete week 48 assessments or have early terminated. At that time, the database related to the end of treatment analyses will be cleaned, processed and a snapshot will be taken.

7.4 Final Analysis

Final analysis will be performed when all randomized subjects either complete the extended safety follow-up and ended the study or early terminate from the study. At that time, the database related to the final analysis will be cleaned, processed and the database will be locked. All efficacy and safety analyses during the extended follow-up period will be performed.

8. Data Screening and Acceptance

